## Purpose and Aims

DRG stimulation is today considered a standard therapy for several neuropathic pain conditions. Despite its widespread clinical use, a critical knowledge gap remains: the efficacy of DRG stimulation has never been validated against sham in a controlled trial. The only randomized controlled study conducted to date is an industry-sponsored comparison between DRG stimulation and spinal cord stimulation (SCS) (9), but no trial has directly tested DRG against placebo.

Umeå University Hospital is internationally recognized as a leading center for DRG stimulation. Patients from across Sweden are referred to our department, making our clinic the de facto national referral center for this therapy. In practice, DRG therapy is centralized to our unit. The resulting high patient volumes, together with our long-standing expertise and comprehensive quality database, provide unique opportunities to fill this knowledge gap—opportunities that no other center is currently positioned to offer.

The purpose of this study is therefore to rigorously evaluate whether ongoing sub-threshold DRG stimulation provides genuine analgesic benefit beyond contextual or placebo effects. Sub-threshold programming is already the accepted standard within DRG stimulation, but the specific contribution of this approach remains to be clarified in a placebo-controlled setting. Addressing this knowledge gap will provide robust scientific evidence to support or refute the physiological efficacy of sub-threshold DRG stimulation.

Our primary aim is to determine the impact of sub-threshold DRG stimulation on pain intensity in established responders, using a double-blind, crossover design. Secondary aims include assessing effects on sleep, mood, and activity, as well as evaluating the feasibility of maintaining blinding and capturing safety and tolerability data.

## Significance

The efficacy of DRG stimulation has never been validated in a sham-controlled trial, leaving a critical knowledge gap that this study seeks to address. Without placebo-controlled evidence, the true physiological contribution of DRG stimulation remains uncertain and current clinical guidelines are built on a limited scientific foundation.

By conducting the first sham-controlled trial of DRG stimulation in this setting, we can generate definitive evidence on efficacy and safety, with findings likely to influence clinical practice and policy both nationally and internationally. The results will directly inform clinical guidelines, payer decisions, and programming strategies, and they will strengthen the scientific foundation of DRG stimulation as a safe, effective, and durable treatment for neuropathic pain.

## Background & Rationale

Neuropathic pain affects roughly 6–10 % of the adult population and is notoriously refractory to pharmacotherapy, leaving many patients with disabling pain, sleep disturbance and mood disorders. Aberrant ectopic firing in the dorsal root ganglion (DRG)—where primary afferent somata reside—has been identified as a key generator and amplifier of neuropathic signalling (1–5). Therapeutically targeting the DRG is therefore conceptually attractive: modulating neuronal activity at this choke-point can quell both peripheral hyperexcitability and downstream central sensitisation.

Dorsal root ganglion stimulation (DRG-S) delivers biphasic electrical pulses via percutaneously placed leads anchored inside the intervertebral foramen. Unlike conventional spinal cord stimulation (SCS), in which lead migration and rostro-caudal current spread often blur coverage, each DRG occupies a stereotyped position and maps to a discrete dermatome. This anatomic precision translates into highly focal pain relief, fewer unwanted paraesthesiae and reduced energy consumption (6,7). Over the past decade, DRGS has progressed from an experimental therapy to an established treatment for complex regional pain syndrome (CRPS), causalgia, postsurgical and post-traumatic pain, failed back surgery syndrome and chronic low-back pain (8–14). Contemporary consensus guidelines explicitly recommend sub-threshold programming as the default setting, citing improved patient comfort and comparable efficacy (6,7). Contemporary consensus recognises sub-threshold stimulation as an accepted and widely applied programming technique within DRG stimulation.

While early systems relied on supra-threshold amplitudes that elicited paresthesia, modern programmers default to sub-threshold output because patients find the absence of tingling more acceptable and battery longevity improves without an apparent loss of efficacy (9,12,19). Animal data suggest that tonic sub-threshold fields preferentially depress spontaneous DRG firing, inhibit dorsal horn wide-dynamic-range neurons and normalize thalamocortical connectivity—all without recruiting large-diameter A $\beta$  fibers thought to mediate paresthesia (19). Yet the true clinical contribution of these physiological effects is unknown because, to date, no double-blind, sham-controlled randomized trial has directly compared DRG-S with placebo. Existing evidence consists mainly of open-label cohorts or active-control designs (e.g., DRG-S versus SCS), which cannot disentangle treatment benefit from expectation, interaction or regression to the mean. To our knowledge, no previous double-blind, randomized, and sham-controlled trial has specifically investigated DRG stimulation, highlighting the novelty of the present design.

The present study addresses this critical knowledge gap. By enrolling patients who have already demonstrated durable (> 3 months) and substantial ( $\geq 50\%$ ) pain relief on DRG-S and randomizing them to short crossover periods of sub-threshold stimulation or sham, we can isolate the physiological effect of ongoing DRG-S while minimizing ethical concerns and placebo variability. A rigorous sham-controlled, crossover design will provide high internal validity and maximize power with a modest sample size. The resulting evidence will clarify whether sub-threshold DRG-S delivers genuine analgesia beyond contextual factors and will inform future guideline recommendations, payer decisions and programming algorithms. Testing in established responders is desirable to ensure safety, feasibility, and parameter optimization, and to confirm the capacity to maintain blinding. As a subsequent step following this trial, we plan to conduct a randomized, blinded study in de novo patients to validate efficacy in a primary implantation population.

## Preliminary Results

Umeå University Hospital is internationally recognized as one of the leading centers in the world for DRG stimulation. Over the past decade, our department has established a comprehensive quality database with structured, prospective data collection, including patient-reported outcome measures (PROMs), patient-reported experience measures (PREMs), detailed device and implant information, and systematic adverse event reporting.

This database currently includes more than 100 patients with active DRG therapy, representing what is likely the largest clinical cohort worldwide. The longest follow-ups now exceed five years (Appendix 1: Data report from our quality database). Analyses of these data indicate that DRG stimulation is a safe and effective treatment for a broad spectrum of neuropathic pain conditions, with consistent and long-lasting analgesic effects. Our findings further suggest that treatment durability extends beyond pain reduction, positively influencing function, mood, and quality of life. Importantly, a comprehensive retrospective analysis of these data is being finalized and will be published during the second half of 2025, further underscoring the robustness and maturity of our clinical experience.

This extensive real-world experience and infrastructure provide a unique foundation for the proposed trial, ensuring feasibility, robust recruitment, and reliable follow-up. Moreover, our track record demonstrates both the scientific and clinical capability of our team to conduct a sham-controlled study of this scope with high internal validity.

## Objectives & Hypotheses

- Primary Objective – To compare mean daily pain intensity during five days of sub-threshold DRG stimulation versus sham.
- Secondary Objectives – To compare sleep quality, mood, and daily activity between conditions; to assess safety and tolerability; to explore within-subject carry-over effects.
- Primary Hypothesis – Sub-threshold DRG stimulation will reduce mean Numeric Rating Scale (NRS, 0–10) pain scores compared with sham.

## Study Design

- Randomized, double-blind, two-period crossover.
- Two treatment arms of 5 days each, separated by a 24 h wash-out.
- Order of conditions (Active → Sham or Sham → Active) allocated 1:1 using computer-generated random blocks.
- Participant, treating clinician, and outcome assessors blinded.

## Participant Selection

### Inclusion Criteria

1. Adults ( $\geq 18$  y) with an implanted DRG stimulator for a chronic neuropathic pain condition (not necessarily focal).
2.  $\geq 50$  % pain reduction sustained for  $\geq 3$  months on standard (supra-threshold) therapy.
3. Stable analgesic regimen  $\geq 4$  weeks.
4. Ability to comply with diary completion and study visits.

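### Inclusion 2 requires response on supra-threshold therapy, but the stated purpose is to test ongoing sub-threshold stimulation, which the protocol elsewhere calls the standard

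*Combined protocol and SAP*

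**What the plan says.** The protocol uses the word *standard* for two opposite programming modes.

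- **Inclusion Criteria, item 2:** the qualifying relief must have lasted at least 3 "months on standard (supra-threshold) therapy".
- **Purpose and Aims:** "Sub-threshold programming is already the accepted standard within DRG stimulation". The study is to "rigorously evaluate whether ongoing sub-threshold DRG stimulation provides genuine analgesic benefit beyond contextual or placebo effects". The primary aim in the same section is to "determine the impact of sub-threshold DRG stimulation on pain intensity in established responders", with no mode named for the earlier response.
- **Background & Rationale:** "Contemporary consensus guidelines explicitly recommend sub-threshold programming as the default setting", and "While early systems relied on supra-threshold amplitudes that elicited paresthesia, modern programmers default to sub-threshold output". Enrolling responders is justified because in this way "we can isolate the physiological effect of ongoing DRG-S while minimizing ethical concerns and placebo variability". Here too the mode of the earlier response is left open.
- **Interventions:** the active condition is an amplitude titrated to 80 % of perception threshold, with frequency and pulse-width left as in clinical use. Sham is the device switched off.
- **Study Schedule & Assessments:** perception threshold is recorded at screening, the device is off for 24 h from Day 0, and Period 1 starts on Day 1.

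**The concern.** Enrolling only established responders works best when the therapy being withdrawn or continued is the one on which they responded. The rationale relies on this when it speaks of isolating the effect of ongoing therapy. Inclusion 2, as worded, ties the response to a different amplitude range from the one under test.

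Two things are at stake. The first is interpretation: the purpose promises an answer about ongoing sub-threshold therapy, and the Significance section expects the results to inform guidelines, payers and programming strategies. The population behind that answer should therefore be clear. The second is conduct. One screener could apply the criterion literally while another follows the Background and admits sub-threshold responders. That would give an unplanned mixture, and no scheduled assessment names the habitual mode that would be needed to separate the two groups.

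**Working it through.** No figure in the plan depends on this wording, so the check is a comparison of the text.

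| Question | Section | Answer |
|---|---|---|
| Which mode is standard? | Inclusion Criteria, item 2 | Supra-threshold |
| Which mode is standard? | Purpose and Aims | Sub-threshold |
| Which mode is the default? | Background & Rationale (two places) | Sub-threshold; supra-threshold is assigned to early systems |
| What is tested? | Purpose and Aims | Ongoing sub-threshold stimulation |
| What is tested? | Objectives & Hypotheses | Sub-threshold versus sham, without the word ongoing |
| On which mode must response have been shown? | Purpose and Aims (primary aim); Background & Rationale | Not stated |
| On which mode must response have been shown? | Inclusion Criteria, item 2 | Supra-threshold |

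**Step 1: who is eligible on a literal reading.** A patient whose relief of at least 50 % was obtained on supra-threshold output qualifies. A patient with the same relief on sub-threshold output does not.

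**Step 2: what happens to those enrolled.** Supra-threshold output lies above perception threshold by definition, and the active setting is 80 % of that threshold. The amplitude is therefore lower than the habitual one for every literally eligible participant. Active is a new setting and not a continuation.

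**Step 3: is there a run-in or a response check at the new setting?** The schedule lists none. The only lead-in is 24 h with the device off. The pre-trial detection test under Randomisation & Blinding Procedures uses one-minute sessions in 10 participants and asks about paresthesia, so it does not check analgesia. Exclusion 3 bars planned stimulation adjustments from two weeks before enrolment onward. It presumably means adjustments outside the protocol, and it does not supply a run-in either.

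**Step 4: what each result would mean on that reading.**
- *Null:* either sub-threshold stimulation adds nothing over sham, or these patients lose benefit when amplitude is lowered although patients established on sub-threshold output would not. The design cannot tell these apart.
- *Positive:* sub-threshold stimulation beats sham over short periods in patients converted from supra-threshold therapy. That is a valid finding, but it is not evidence on ongoing sub-threshold therapy.

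**Step 5: the alternative reading.** If the parenthesis is a slip, the population and the purpose agree and steps 1 to 4 fall away. The wording of an operative criterion would still be wrong. The documents do not show which reading is intended, nor how many patients in the centre's database use each mode.

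**The case against.** The strongest reply is that the mismatch depends on one adjective. *Ongoing sub-threshold* appears in the purpose sentence. The formal objective and hypothesis compare sub-threshold stimulation with sham and do not require prior sub-threshold use. Supra-threshold responders are still established responders to this therapy, with the same implant, frequency and pulse-width. The Background also asserts comparable efficacy and no apparent loss when output is sub-threshold. The parenthesis may be no more than a slip.

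Much of this stands. The randomised contrast is internally valid in whichever population is enrolled, and the enrichment is weakened rather than abolished. But comparable efficacy between modes is background opinion; the protocol itself says the contribution of sub-threshold programming has yet to be clarified against placebo. The reply also does not remove the contradiction. If supra-threshold is intended, the purpose and the rationale need rewording; if it is not, the criterion does.

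A reader might go further and infer a definite loss of power, supposing that some fraction of participants gets no benefit at the lower amplitude. The documents give no such fraction and no effect size by mode; the 1-point difference in the Statistical Analysis Plan is a minimally important difference, not an observed effect. A reader might also infer a recruitment problem. The protocol reports more than 100 patients on active therapy against a target of 28 but gives no split by mode, so this cannot be shown.

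**Conclusion.** The contradiction is in the current text, and it sits in an eligibility rule, so it should be settled before the first participant is enrolled. On the literal reading the trial enrols people for whom the active setting is new, and its result would describe short-term conversion rather than the ongoing therapy named in the purpose.

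Its size cannot be put in numbers from these documents. The enrichment is weakened by an unknown amount, and a null result becomes ambiguous. These consequences assume that Inclusion 2 is applied as written. If the parenthesis is a slip, only the wording needs correcting.

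A reader might infer that the trial cannot answer its question at all. That is not supported: the sub-threshold versus sham comparison in Objectives & Hypotheses remains sound, and a positive result would be real evidence in the population enrolled. What fails is the match between that population and the stated purpose.

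**What to change.** Before enrolment:

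1. Reconcile Inclusion Criteria item 2 with Purpose and Aims, Background & Rationale and Interventions, so that *standard* has one meaning throughout.
2. State in Inclusion 2 the stimulation mode or modes on which the qualifying response must have been shown.
3. Make the purpose, objective and planned conclusion name that same population: patients continuing sub-threshold therapy, patients converted from supra- to sub-threshold, or both.
4. Record each participant's habitual amplitude at screening, relative to the perception threshold already recorded there.
5. If both modes are admitted, report the treatment effect by habitual mode, descriptively only. With 24 planned completers a formal subgroup comparison is not realistic. If only one mode is admitted, no such breakdown applies.

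Which mode is clinically right is for the sponsor to decide. The cost is a wording amendment and one added screening field, since the schedule lists the perception threshold but not the habitual amplitude. The downside is that the claim may have to be narrower than the purpose now promises.

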### Exclusion Criteria

1. Active infection or wound complication at implant site.
2. Significant psychiatric comorbidity (e.g. uncontrolled depression, psychosis).
3. Planned surgery, stimulation adjustments, or medication changes within 2 weeks prior to enrolment or at any time during the study period.
4. Pregnancy or breastfeeding.
5. Occurrence of any adverse event during the study that meets the predefined withdrawal criteria (see Safety Monitoring); such participants are withdrawn immediately and not re-randomized.

### Interventions

- Active Sub-Threshold Stimulation – Device amplitude individually titrated to 80 % of perception threshold (no paresthesia felt), frequency and pulse-width unchanged from clinical settings.
- Sham – Stimulator switched off. Device interrogation logs masked from participants and outcome staff.

## Randomisation & Blinding Procedures

Randomization is generated automatically within the Patientkollen® patient-management platform using concealed permuted blocks (1:1 allocation) and stored entirely inside the single-site environment at Umeå University Hospital; no files are exported outside the platform.

To maintain blinding: After each treatment period, participants will be asked whether they experienced any paresthesia during the preceding stimulation phase, in order to assess whether the study was genuinely blinded. We will not ask participants to identify whether they believe the period involved sham or active stimulation, as such judgements could be influenced by perceived analgesic benefit. Prior to study initiation, a pre-trial acute detection test will be performed in 10 participants: each will undergo 10 randomized one-minute sessions (stimulator ON at 80% perception threshold or OFF), and after each session indicate whether or not paresthesia was perceived. This will ensure the feasibility of maintaining blinding in the main trial. The programming nurse makes all parameter changes while the participant's handheld programmer is hidden from view.

- After programming, the handheld unit is *locked* with a unique access code known only to the nurse and stored in the electronic Trial Master File (eTMF).
- In a documented emergency (e.g. device-related adverse event or intolerable pain), the code may be disclosed by an investigator uninvolved in outcome assessment. Disclosure automatically withdraws the participant from the study; the reason is logged in the eTMF.

Unblinding procedure: Once the final participant completes Day 10, Patientkollen runs automated integrity checks (range, consistency, missing-value rules) and locks the dataset. The platform then executes predefined statistical scripts comparing sequence labels A and B without human intervention. After the automated analysis is complete, the research team convenes, and the programming nurse activates the “reveal” function in Patientkollen to link each label to its actual treatment order. The validated dataset, analysis outputs, and audit trail then become accessible to the full study group.

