## Statistical Analysis Plan

- Sample Size – Assuming within-subject SD = 1.5 NRS points, minimally important difference = 1 point,  $\alpha = 0.05$ , power = 0.90, two-sided paired test → 24 completers needed (calculated with G\*Power). To accommodate 15 % attrition, target enrolment = 28.
- Primary Analysis – Paired t-test (or Wilcoxon signed-rank if non-normal) comparing mean NRS pain across days 3–5 between Active and Sham periods. If a period is aborted due to high pain, the last recorded score will be carried forward for the remaining days. Treatment order and carry-over tested via mixed-effects model with fixed effects for treatment, period, and sequence.
- Secondary Outcomes – Similar within-subject comparisons; Bonferroni correction applied.
- Missing Data – Multiple imputation if > 5 % diary fields missing.

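### The locked script is described as comparing treatment orders A and B, while the SAP's primary analysis compares Active with Sham within participants; the plan does not connect the two

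*Combined protocol and SAP*

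**What the plan says.** Randomisation & Blinding Procedures (unblinding paragraph) describes the automated run after dataset lock: "The platform then executes predefined statistical scripts comparing sequence labels A and B without human intervention". The programming nurse then activates a reveal function "to link each label to its actual treatment order". A and B are therefore orders. Study Design defines the two orders: "Order of conditions (Active → Sham or Sham → Active) allocated 1:1 using computer-generated random blocks".

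Statistical Analysis Plan, Primary Analysis, specifies a paired t-test, or a Wilcoxon signed-rank test if the data are non-normal, "comparing mean NRS pain across days 3–5 between Active and Sham periods". A separate model is added: "Treatment order and carry-over tested via mixed-effects model with fixed effects for treatment, period, and sequence". Objectives & Hypotheses frames the question as stimulation against sham.

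The unblinding paragraph does not name the outcome variable, the test or the model that the script applies to A and B. The Statistical Analysis Plan does not say how its contrast is formed while the labels are masked.

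**The concern.** In a two-period crossover, order and treatment are different factors. Every participant in A and every participant in B receives both conditions, so comparing A with B on pain over the whole trial is a between-participant comparison from which treatment drops out. What remains is a test of sequence, which in this design is informative only about differential carry-over or chance imbalance between the groups.

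The timing makes this matter. The script runs without human intervention, and its outputs become accessible to the study group only after the reveal. If it has been programmed from the unblinding paragraph alone, the mismatch would be found once treatment order is known. Choosing or re-running the primary test at that point is what the hands-off run is meant to prevent.

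**Working it through.** **Inputs.** From the Statistical Analysis Plan: SD 1.5, difference 1 NRS point, two-sided alpha 0.05, power 0.90, 24 completers. From Study Design: two orders, 1:1, hence 12 + 12. Assumed, because the documents give no value: between-participant SD 1.5, period effect 0 to 1 point, no differential carry-over.

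**1. The plan's own figure.** Taking 1.5 as the SD of the paired differences, n = (1.5 × (1.960 + 1.282) / 1)² = 23.6, so 24. This reproduces the stated number by the normal approximation. The noncentral t distribution gives power 0.878 at 24.

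**2. What A versus B contains.** Let δ be the reduction under Active, π the period effect, μ the Sham mean in Period 1, and let A be Active first.

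| | Period 1 | Period 2 | Participant mean | Period 1 − Period 2 |
|---|---|---|---|---|
| A | μ − δ | μ + π | μ + (π − δ)/2 | −δ − π |
| B | μ | μ + π − δ | μ + (π − δ)/2 | δ − π |

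- Participant means: A − B = 0, whatever δ is.
- Period differences: A − B = −2δ, and half of this is −δ, free of π.
- If A is in fact Sham first, the second result changes sign and nothing else changes. The two-sided p-value is the same under either labelling.

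**3. Analytic power at δ = 1.**

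- Period differences between orders: noncentrality 2 / (1.5 × √(2/12)) = 3.27 on 22 df, power 0.877.
- Paired Active − Sham: noncentrality √24 / 1.5 = 3.27 on 23 df, power 0.878.

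The two tests differ by one degree of freedom.

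**4. Simulated rejection rates (40,000 trials each, δ = 1).**

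| Period effect | A vs B, participant means | A vs B, period differences | Paired Active − Sham | Last two disagree on significance |
|---|---|---|---|---|
| 0 | 5% | 88% | 88% | 0.9% |
| 0.5 | 5% | 88% | 85% | about 3% |
| 1 | 5% | 88% | 77% | about 11% |

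With δ = 2 the first comparison still rejects in 5% of trials. A comparison of A with B on Period 1 alone would reject in 25% at δ = 1 (36% to 18% for a between-participant SD of 1 to 2).

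**5. Why the paired test loses power.** The Active − Sham difference has mean −δ − π in A and −δ + π in B. Pooling the two groups inflates the estimated variance to about 1.5² + π² × 24/23. At π = 1 this is 2.25 + 1.04 = 3.29, an SD of 1.81 instead of 1.5.

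**The case against.** The strongest reply is that the unblinding paragraph describes a procedure and sets out no rival primary test. It calls the scripts predefined, and the only analyses predefined anywhere are those in the Statistical Analysis Plan. On this reading, the script runs the paired Active–Sham analysis while the key is masked. That is feasible, because order label plus period identifies the condition up to one global swap. Comparing orders on period differences is moreover the standard treatment test for this design. The 5% figure belongs to an analysis of participant means that no section names.

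Most of this stands. A reader might infer from the wording that the trial will test sequence and not treatment. The documents do not support that: the compared variable is unnamed, and the correct contrast is pre-specified elsewhere. The 5% is the consequence of one literal reading and does not describe the plan as a whole.

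The reply does not remove the inconsistency. The reader has to supply the step from masked orders to the treatment contrast. The charitable reading is also not one identifiable test. A two-group comparison of period differences is not the paired t-test, and its rank-based counterpart is a rank-sum test, whereas the plan names the signed-rank test. The two valid tests can reach different conclusions, as step 4 shows.

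**Conclusion.** The concern holds as an inconsistency between two sections about what the locked script compares. The unblinding paragraph names treatment orders; the Statistical Analysis Plan names conditions within participants; no text connects them. On the literal reading (A against B on overall pain) the treatment effect is not estimated, and the rejection rate is about 5% whatever its size. On the workable reading the treatment contrast is available up to sign with about 88% power at 24 completers. The documents do not say which reading will be programmed.

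These figures assume 12 + 12 completers, an SD of paired differences of 1.5, a 1-point effect and no differential carry-over. The 77% for the unadjusted paired test depends on an assumed 1-point period effect. The point should be settled before the script is locked. It does not undermine the design, and it does not change the sample size.

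**What to change.** Amend two places so that they name the same single test.

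- **Randomisation & Blinding Procedures, unblinding paragraph:** state that the script runs the primary treatment contrast under masked labels, and that the reveal supplies only its direction.
- **Statistical Analysis Plan, Primary Analysis:** name the outcome variable, the labels and the model. Preferably this is the within-participant Period 1 − Period 2 difference compared between masked orders, with half the between-order difference as the estimate. Equivalently, use masked condition codes X and Y assigned by period, in a model with participant, treatment and period.

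The sponsor has to choose one. The paired t-test now named has no period term, so the script cannot both run that test unchanged and adjust for period. If period differences are chosen, the rank-based fallback becomes a rank-sum test between orders. The existing mixed model can stay as the supporting analysis of order and carry-over.

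The cost is a sentence or two in each section, a relabelled variable in the script and one degree of freedom (0.877 against 0.878 power with no period effect). The gain is 88% against 77% power if the period effect is 1 point.
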